11.6.1.2 Mixed Effect Regression Model

A mixed effects regression model using a covariance pattern will be fitted to the absolute change from baseline mean NPRS scores at weeks 1, 2, 3 and 4 within each treatment period for the PP population. This analysis will provide the results for the primary efficacy endpoint (change from baseline to week 4) and for the secondary endpoint (change from baseline to weeks 1, 2 and 3).

The model will have fixed effects for period, week, treatment and the interaction between week and treatment. Baseline mean pain score within each period by treatment combination will be included as a covariate. A random effect for subject will be included to capture the repeated measures nature of the design.

Least squares means and corresponding 95% confidence intervals (CI) will be presented for the mean change from baseline for LAT8881, Placebo and difference between LAT8881 vs. placebo at each visit.

P-values for testing the null hypothesis that the difference in least squares means between LAT8881 and placebo at each visit is 0 will be declared statistically significant if the p-value < 0.05.

The covariance pattern will take into account the covariance between observations in different treatment periods and the covariance between observations within the same period (i.e between weeks).

```
proc mixed data=;  
class <subject> <study period> <treatment> <week>; model  
<change> = <baseline> <study period> <week> <treatment>;  
random <subject> <subject>*<period>; lsmeans <treatment>  
<week> / pdiff;  
run;
```

The model will also be fitted to the absolute change from baseline in mean NPRS ratings for the FAS population. Extent of sensitivity analyses of missing data patterns to be undertaken will be decided during the blinded review meeting. In DDP: Tables 14.2.2.1 to 14.2.2.2

11.6.1.2.1 *NPRS at timepoints*

A mixed effects regression model using a covariance pattern will be fitted to the absolute change from pre-dose NPRS scores at timepoints 0.5, 1, 2, 4 and 6 hours post-dose at baseline and week 4 visits within each study period for the per-protocol subjects with NPRS collected at timepoints in baseline and week 4 visits.

The model will have fixed effects for period, week, timepoint and the interaction between week and timepoint. Pre-dose pain score within each week will be included as a covariate. A random effect for subject will be included to capture the repeated measures nature of the design.

Least squares means and corresponding 95% confidence intervals (CI) will be presented for the mean change from pre-dose for each timepoint at each visit. P-values for testing the null hypothesis that the difference in least squares means across timepoints at each visit will be declared statistically significant if the p-value < 0.05.

The covariance pattern will take into account the covariance between observations in different treatment periods and the covariance between observations within the same period (i.e between weeks).

```
proc mixed data=;  
class <subject> <timepoint> <week>; model  
<change> = <baseline> <week> <timepoint>; random  
<subject> <subject>*<week>; lsmeans <timepoint>  
<week> / pdiff; run;
```

In DDP: Tables 14.2.2.3

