13.5.1 NPRS

The primary efficacy endpoint is the absolute change from baseline mean NPRS score to the end of treatment NPRS score after LAT8881, compared with the change from baseline after placebo treatment.

Daily NPRS scores for all enrolled subjects will be listed only. Mean and standard deviation of scores during the baseline period and weeks 1, 2, 3 and 4, and the absolute and percentage change from baseline in each period, will be listed for each subject and summarised for LAT8881 and placebo treatments overall and within treatment sequence for all randomised subjects and for the PP population. The maximum change in mean NPRS from baseline to weeks 1, 2, 3 and 4, determined for each subject after LAT8881and placebo, will be listed and summarised.

Mixed effects regression models will be used to compare the absolute and percentage changes from baseline to the end of each treatment for the mean NPRS scores. The models will have fixed effects for period and treatment. Baseline mean pain score within each period by treatment combination will be included as a covariate. A random effect for subject will be included to capture the repeated measures nature of the design.

The models for the primary endpoint will be expanded to compare the absolute and percentage changes from baseline for the mean NPRS scores after 1, 2 and 3 weeks of dosing with IMP in each treatment period. The model will also include a fixed effect for week (1, 2, 3 and 4), the interaction between treatment and week to assess whether the change from baseline for each treatment is different.

The mean score at each visit, change from baseline, difference between treatments in the change from baseline and corresponding 95% confidence intervals will be presented. Comparisons will be declared statistically significant if p<0.05.

In PK subjects, NPRS scores at specified times up to 6 hours on Days 1, 28, 50 and 77 will be listed and summarised. Change from pre-dose values will also be listed and summarised. Changes over time will be analysed using the same modelling approach as for the primary endpoint.

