11.7.3.4 Electrocardiogram Assessments

Number and percentage of subjects with overall findings (Normal, Abnormal Not CS and Abnormal CS) will be summarized by treatment overall and within each study period and visit. Percentages will be based on safety population.

In DDP: Table 14.3.6.1

ECG findings will be listed by treatment sequence, subject ID, treatment period and visit.

In DDP: Listing 16.2.9.3

12 Changes to Planned Analyses

- Mixed Effect Regression analyses for change from baseline in NPRS mean scores is combined for weeks 1-4 within the same model, instead of week 4 and weeks 1-3 separately as defined in study protocol.
- McNemar's test is included to compare proportion of subjects achieving $\geq 30\%$ and $\geq 50\%$ reduction in mean NPRS scores across study periods.
- Analysis of covariance is included to see the effect of treatment and placebo in maximum reduction from baseline adjusting for baseline NPRS mean scores and time taken to reach maximum reduction.
- Mixed Effect Regression analyses for change from baseline in NPRS mean scores including clinical diagnosis (PHN, DPN) and baseline [REDACTED] as additional covariates is

considered as secondary analyses instead of exploratory analyses since subgroups PHN and DPN were considered clinically relevant.

- PK Analyses is not included in this Statistical Analysis Plan, and will be done separately. PK Population is replaced with Per-Protocol population for subjects with NPRS assessments taken at timepoints in baseline and Week 4 visits.

13 Index of Tables, Listings and Graphs

Refer LAT-NP-001_Data Display Plan (Ver: 2.00) for the list of Tables, Listings and Graphs.

14 References

1. ICH. ICH Harmonized Tripartite Guideline: Statistical Principles for Clinical Trials E9. 1998.
2. ICH. ICH Harmonized Tripartite Guideline: Structure and Content of Clinical Study Reports E3. 1995.

15 Appendices

15.1 painDETECT questionnaire

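### The timepoint NPRS model (SAP 11.6.1.2.1) has no treatment term, so it cannot address secondary objective 1; separately, the primary model's code omits the week-by-treatment interaction that its own text requires

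*SAP*

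**What the plan says.** **Timepoint model (SAP 11.6.1.2.1).** Secondary objective 1 (SAP 3.2, Protocol 4.2) is a comparison of LAT8881 with placebo over six hours after a single dose and again after four weeks, in PK subjects. Protocol 13.5.1 says that these changes are to be modelled in the same way as the primary endpoint. The SAP text lists fixed effects for period, week, timepoint and week-by-timepoint, with the pre-dose score as covariate and a random subject effect. Its outputs are a mean change for each timepoint at each visit and a test of differences across timepoints. The code has baseline, week and timepoint in MODEL, and subject and subject-by-week in RANDOM. The matching descriptive summary (SAP 11.6.1.1.1) is laid out by study period and total.

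**Main NPRS model (SAP 11.6.1.2).** On its purpose, the text says "This analysis will provide the results for the primary efficacy endpoint (change from baseline to week 4"), with weeks 1 to 3 as secondary results. On its terms: "The model will have fixed effects for period, week, treatment and the interaction between week and treatment". It asks for an estimate, confidence interval and p-value for the "difference between LAT8881 vs. placebo at each visit". The code that follows has "class <subject> <study period> <treatment> <week>; model", then "<change> = <baseline> <study period> <week> <treatment>", then "random <subject> <subject>*<period>; lsmeans <treatment>", with week as the only other LSMEANS effect and PDIFF as the only option.

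**Protocol 13.5.1** has two models. The stand-alone end-of-treatment model has period and treatment, a baseline covariate and a random subject effect. Of the expanded weekly model it says: "The model will also include a fixed effect for week (1, 2, 3 and 4), the interaction between treatment and week". SAP section 12 records that the NPRS analysis "is combined for weeks 1-4 within the same model, instead of week 4 and weeks 1-3 separately as defined in study protocol". It does not mention dropping the interaction, or dropping treatment from the timepoint model.

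**The concern.** A model without a treatment term cannot estimate a treatment difference. In a crossover, a timepoint mean without treatment in the model averages the LAT8881 and placebo responses of the same people. As the timepoint section stands, following its text exactly and following its code exactly both leave secondary objective 1 without a model-based answer.

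In the main model, leaving out week-by-treatment forces one treatment difference on all four weeks. LSMEANS on the two main effects then prints that single difference and the week-versus-week differences, but no treatment contrast at week 4. The pooled and week 4 differences agree only if the effect is the same in every week. PDIFF without CL also does not print the confidence intervals that the text requires. The same model is reused for percentage change (SAP 11.6.2.1), clinical diagnosis (11.6.2.5) and baseline variability (11.6.3.2), so a slip in the code could carry over to those analyses.

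**Working it through.** **A. Timepoint model: terms side by side**

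| Term | SAP text | SAP code | Needed for objective 1 |
|---|---|---|---|
| Pre-dose score | yes | yes | yes |
| Period | yes | no | yes |
| Week (visit) | yes | yes | yes |
| Timepoint | yes | yes | yes |
| Week by timepoint | yes | no | yes |
| Treatment | no | no | yes |
| Treatment with week and timepoint | no | no | yes |

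Differences needed: 5 timepoints x 2 visits = 10. Differences delivered by text or code: 0. With balanced data, a change of 1 point on LAT8881 and 0 on placebo appears as one timepoint mean of (1 + 0)/2 = 0.5. The documents give no variance for these ratings, so no power figure is offered.

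**B. Main model: what the code would deliver if followed**

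*Inputs from the documents* (Protocol 13.2 and synopsis; SAP 4.2 and 8): SD of change 2, correlation between active and placebo 0.5, difference 1 point, two-sided 5%, 44 evaluable subjects, 20% dropout.

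*Assumptions not in the documents:* the weekly effect profile, the within-period correlation between weeks (rho_w, 0.6 to 0.9), and complete data.

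1. Plan's own figure. SD of the paired difference = 2 x sqrt(2 x (1 - 0.5)) = 2.0. SE = 2.0/sqrt(44) = 0.302. Noncentral t power on 43 df = 90.0%. Recruitment = 44/(1 - 0.20) = 55. Both stated figures reproduce, and they rest on a single end-of-treatment difference.
2. Target of the coded model. With complete data it is the simple average of the four weekly differences. For a building profile: (0.25 + 0.50 + 0.75 + 1.00)/4 = 0.625, against 1.00 at week 4.
3. SD of the paired four-week average. Paired differences have variance 4 within a week and covariance 8 x (rho_w - 0.5) between weeks. The variance of their mean is therefore [4 + 3 x 8 x (rho_w - 0.5)]/4 = 2 x (3 x rho_w - 1).
4. Power with 44 pairs, by noncentral t:

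| rho_w | SD | SE | Constant 1 point | Building to 1 (estimate 0.625) | Waning evenly from 1 to 0 (estimate 0.50) |
|---|---|---|---|---|---|
| 0.6 | 1.265 | 0.191 | 99.9% | 89.3% | 72.7% |
| 0.7 | 1.483 | 0.224 | 99.2% | 78.0% | 58.9% |
| 0.8 | 1.673 | 0.252 | 97.2% | 67.8% | 49.1% |
| 0.9 | 1.844 | 0.278 | 94.0% | 59.4% | 42.0% |

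The last column is a constructed worst case, with no effect at week 4. A week 4 test would be significant 5% of the time there. With no effect in any week, the coded model also keeps its 5% level.

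5. Check by fitting. In one simulated crossover of 4,000 subjects with the building profile, the model as coded gave a difference of 0.62. With week-by-treatment added, the week 4 difference was 1.01 (true value 1.00).

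**The case against.** The strongest reply is that the primary method is stated correctly. The text of SAP 11.6.1.2 names the interaction, asks for differences at each visit and makes week 4 primary. The code is a template with placeholders, and the Data Display Plan, which is not among the documents, may have table shells that would expose the slip. This stands. A reader might infer that the primary analysis is mis-specified or that its result will be a four-week average. The documents do not support that, because it happens only if the code is followed over the text. Still, nothing labels the code as illustrative, and in SAP 11.6.2.2.1, 11.6.2.3.1 and 11.6.2.4.2 the coded MODEL terms do match the text.

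A reader might also infer that the protocol requires the interaction in its primary model. It does not: it belongs to the expanded weekly model. It became necessary for the primary result when the SAP merged the two.

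The sizes in part B rest on assumed profiles and correlations, and a constant effect costs nothing.

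On the timepoint analysis, the planned PK subset is only 15 subjects and SAP 8.3 already urges caution with secondary tests. Both limit the weight of the point, but neither supplies a treatment comparison. It is also tempting to say that the descriptive summary is plainly not by treatment. SAP section 11 has a general rule that summaries other than four listed ones are by treatment overall and within periods, so SAP 11.6.1.1.1 is ambiguous rather than wrong.

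The two placeholders for period, in RANDOM and in CLASS and MODEL, are housekeeping only.

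**Conclusion.** Both parts are wrong as written and worth correcting before unblinding; they differ in kind.

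The timepoint gap does not depend on which text is followed. Neither the prose nor the code gives any of the 10 comparisons with placebo, and section 12 declares only the change of population for these subjects and the separate handling of PK. The consequence is confined to one secondary objective in about 15 subjects.

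The primary-model defect is an inconsistency between code and text, and the code is the part in error. Its harm is conditional. If the code is followed, the building profile gives 0.625 instead of 1.00, with power of 89% to 59% instead of 90%, over assumed between-week correlations of 0.6 to 0.9 and 44 complete pairs. With a constant effect there is no harm. The stated primary method and the sample size of 44 (55 recruited) are unaffected.

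**What to change.** **SAP 11.6.1.2.1 and 11.6.1.1.1.**
- Add treatment and its two-way and three-way interactions with week and timepoint to both text and code.
- Add period and `<week>*<timepoint>` to the code, as the text already lists them.
- Include random terms for subject and for the dosing session (subject by period by visit).
- Rewrite the output and test sentences to report LAT8881 minus placebo with a 95% CI at each timepoint and visit. These are 10 named contrasts out of the 190 pairs among 2 x 2 x 5 = 20 cells.
- Lay out the descriptive summary by treatment.
- If no comparison with placebo is intended, say so in section 12 instead.

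**SAP 11.6.1.2.**
- Add `<week>*<treatment>` to MODEL and use `lsmeans <week>*<treatment> / pdiff cl`.
- Name the week 4 LAT8881 minus placebo difference as the primary test. The 2 x 4 = 8 cells print 28 differences, of which 4 compare treatments within the same week.
- State that the text governs where text and code differ.
- As housekeeping, use one name for the period variable here and in 11.6.2.3.1 and 11.6.2.4.2.

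**Cost.** SAP text, code and some table shells in the Data Display Plan, before unblinding. Data collection, sample size and the stated primary method do not change.

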All subjects will take their second Day 77 IMP dose in the evening. They will be asked to discontinue their IMP after taking the Day 77 evening dose.

End of Study (Day 91)

At the end of study visit, weight, vital signs, a targeted physical examination, concomitant medications and adverse events will be recorded. Blood and urine samples will be taken for safety analysis.

Early withdrawal

Subjects who withdraw early will be asked to attend an end of study visit. This visit should be scheduled approximately two weeks after the last dose was taken.

Statistical Analysis

With a total sample size of 44 evaluable subjects there is 90% power to demonstrate a statistically significant difference in the mean change from baseline NPRS for the active treatment compared with placebo of at least 1 unit. This assumes that the standard deviation of the change from baseline NPRS is 2, the correlation between active and placebo responses within a subject is 0.5 and there is a 2-sided test at the 5% level of significance. Assuming a 20% dropout rate, it is aimed to enrol at least 55 subjects to obtain 44 evaluable subjects.

The number of subjects within each treatment group is also sufficient to show a statistically significant change from baseline of 2 or more points on the NPRS.

The primary efficacy endpoint is the change from baseline mean NPRS score to the end of treatment mean NPRS score after LAT8881, compared with the change from baseline after placebo treatment. This will be analysed in the per protocol (PP) population, which will be defined in a statistical analysis plan (SAP) before database lock. The PP will be based on the duration of IMP treatment and protocol deviations.

Mixed effects regression models will be used to compare the absolute and percentage changes from baseline to the end of each treatment for the mean NPRS scores. The models will have fixed effects for period and treatment. Baseline mean pain score within each period by treatment combination will be included as a covariate. A random effect for subject will be included to capture the repeated measures nature of the design.

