13.2 Sample size

The sample size estimation is based on the following assumptions:

- Power of 90%
- The mean change from baseline NPRS for the active treatment compared with placebo is at least
 1 unit
- Standard deviation of the change from baseline in NPRS pain score is 2
- Correlation between active and placebo response is 0.5
- The test is two sided
- The dropout rate is 20%

The number of subjects within each treatment group is also sufficient to show a statistically significant change from baseline of 2 or more points on the NPRS.

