4.2 Sample Size Justification

It is planned to have 44 subjects complete the study. Assuming a 20% dropout, 55 subjects will be recruited. If the dropout rate is higher than 20%, additional subjects (up to 60 in total) may be recruited at the sponsor's discretion to ensure 44 subjects complete the study.

The sample size estimation is based on the following assumptions:

- *Power of 90%*
- *The mean change from baseline NPRS for the active treatment compared with placebo is at least 1 unit*
- *Standard deviation of the change from baseline in NPRS pain score is 2*
- *Correlation between active and placebo response is 0.5*
- *The test is two sided*
- *The dropout rate is 20%*

The number of subjects within each treatment group is also sufficient to show a statistically significant change from baseline of 2 or more points on the NPRS.

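### The merged weeks 1–4 model gives week 4 a variance pooled over four weeks, so the standard error behind the primary test can be too small or too large

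*SAP*

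**What the plan says.** Protocol 13.5.1 gives the end-of-treatment change its own mixed model, with period, treatment, baseline and a random subject effect. An expanded model then covers the earlier weeks. SAP section 12 records the departure: "Mixed Effect Regression analyses for change from baseline in NPRS mean scores is combined for weeks 1-4 within the same model". SAP 11.6.1.2 says of that model: "A mixed effects regression model using a covariance pattern will be fitted to the absolute change from baseline mean NPRS scores". It adds that the week-4 result from this fit is the primary efficacy result.

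The SAP text names no covariance structure. It says only that covariance between periods and between weeks will be taken into account, and it is silent on whether the variance may differ by week. The printed code has two random terms, "random <subject> <subject>*<period>; lsmeans <treatment>", with no REPEATED statement, no GROUP= option and no DDFM= option. The text lists a week-by-treatment interaction, but the MODEL statement omits it. The LSMEANS request covers the treatment and week main effects only.

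The sample size rests on a single spread: "Standard deviation of the change from baseline in NPRS pain score is 2". Neither document gives SDs by week.

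**The concern.** A week-4-only crossover analysis estimates the week-4 variance from week-4 data. The merged model replaces that estimate with an average over four weeks, because two random intercepts plus one residual variance cannot represent weeks that differ in spread. The primary p-value and confidence interval depend on that figure. If week 4 is more variable than the average, the interval is too narrow and the test exceeds its stated level. If it is less variable, the test loses power. A second, smaller issue is that no degrees-of-freedom method is named, so the reference distribution is left to the software default.

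**Working it through.** **Inputs.** From the protocol synopsis, Statistical Analysis: "With a total sample size of 44 evaluable subjects there is 90% power", a difference "for the active treatment compared with placebo of at least 1 unit", and "there is a 2-sided test at the 5% level of significance". From Protocol 13.2, an SD of 2. From SAP 4.2: "Correlation between active and placebo response is 0.5". Assumed, because the documents do not say: 22 subjects per sequence, complete data, a within-period correlation between weeks of about 0.75, variance changing linearly over weeks, and week-4 SD 2 with week-4 active/placebo correlation 0.5.

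**1. The plan's own figure.** The SD of the within-subject difference is √(2 × 2² × (1 − 0.5)) = 2. The noncentral t gives power 0.9000 (43 df) or 0.8997 (42 df) at n = 44, and 44/0.8 = 55. The stated sample size reproduces. The true standard error of the week-4 contrast is √(4/44) = 0.3015.

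**2. What the merged model reports.** With balanced data, SE² = (2/n)(MS[subject*period]/4 + 3·MSE/4). Its expectation is (2/n)(V − B), where V is the mean of the four weekly variances and B is the mean covariance between periods over all 16 week pairs. The correct value uses week 4 alone: (2/44)(4 − 2) = 0.0909, whose root is 0.3015.

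Two structures keep the correlations constant over weeks:
- (i) Cross-period correlation is 0.5 for every pair of weeks, so B = 0.5 × (mean SD)².
- (ii) Cross-period correlation is tied to the same week, being 0.5 times the within-period correlation. B is then half the mean entry of the within-period covariance matrix.

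Worked example, SD 1.58 rising to 2.00 (variances 2.5, 3, 3.5, 4, so V = 3.25):
- (i) Mean SD 1.796, B = 1.613, SE = √(2 × 1.637/44) = 0.273, about 9–10% too small.
- (ii) Mean entry (0.25 × 13 + 0.75 × 7.184²)/16 = 2.62, B = 1.31, SE = √(2 × 1.94/44) = 0.297.

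**3. Simulated type I error** of the week-4 contrast, using the text's fixed effects (without the baseline covariate), the code's random terms and 258 df:

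| Weekly SD | SE (i) | Error (i) | SE (ii) | Error (ii) |
|---|---|---|---|---|
| Flat at 2.00 | 0.301 | about 5.2% | 0.329 | about 3.5% |
| 2.24 falling to 2.00 | 0.320 | about 4% | 0.349 | about 2.5% |
| 1.84 rising to 2.00 | 0.290 | 6.1% | 0.316 | about 4% |
| 1.58 rising to 2.00 | 0.273 | 7.6–7.8% | 0.297 | 5.7% |

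A week-4-only test stays at 4.7–5.5% in all of these settings.

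**4. The larger figure.** If between-subject variance is held at 2 while total SD rises from 1.58 to 2.00, then V − B = 3.25 − 2 = 1.25. This gives SE = √(2.5/44) = 0.238, which is 21% too small, and type I error of about 12%. It implies a week-1 active/placebo correlation of 2/1.58² = 0.80, falling to 0.50 by week 4.

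**5. Degrees of freedom.** There are 44 × 2 × 4 = 352 observations. The subject-by-period cells use 88 parameters, week uses 3 and week*treatment uses 3, which leaves 352 − 94 = 258. The contrast belongs to the subject-by-period stratum, which has 88 − 44 − 1 − 1 = 42. The critical values are 1.969 and 2.018. A statistic with 42 true df tested against 1.969 has level 5.56%. This assumes that the software falls back on residual df. Satterthwaite df alone hardly help when SDs rise: in one setting with SD 1.4 to 2.0, 9.2% becomes 9.0%.

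**6. Baseline covariate.** A REML fit including it (1,500 trials, within-period correlation 0.7) gave 5.5% with flat SDs and 10.4% with SD 1.4 rising to 2.0. Without it, structure (i) gave 5.0% and 9.2% in the same settings, so the mechanism persists.

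**The case against.** The strongest reply is that direction and size both depend on something the documents do not contain. A reader might infer that the primary test is anti-conservative because change scores spread out as weeks pass, with an error rate of 8–12%. Neither document supports that: there are no weekly SDs, and the plan gives one SD and one correlation. With flat or falling SDs the test is near nominal or conservative. The 12% figure also needs a week-1 correlation of 0.80 that appears nowhere in the plan. This part of the objection stands.

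Second, the printed code lacks the interaction and requests only main-effect means. Run literally, it gives a treatment difference averaged over four weeks, tested at about 5.3–5.8% under default df, and no week-4 contrast at all. The pooled week-4 standard error therefore comes from reading the text's fixed effects with the code's random terms. If the code is only a template, the covariance might be one too. That is fair, but the text names no other structure, so the code is the only specification available.

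Third, the merged model is openly declared, and the protocol's models named no df method either. Also true. But the protocol's week-4 model has one observation per subject and period. It needs no assumption about other weeks, and its residual df are already 88 − 44 − 1 − 1 = 42 (41 with baseline). The merger introduced the problem.

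**Conclusion.** The point holds in a conditional, two-sided form. As specified, the primary standard error borrows its variance from weeks 1–3 and is right only if the weekly variances and between-period covariances fit that structure. With constant correlation structures, the plausible range of type I error is about 2.5–8% around a nominal 5%. The figure of 12% is an extreme that rests on an extra assumption. The df omission is secondary, at no more than about 0.6 points, and depends on an assumed software default.

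These figures assume 44 complete subjects split 22:22 and the correlations listed above. Missing weeks and period-specific per-protocol exclusions were not modelled. The sample size is unaffected: with week 4's own variance and 42 df, power is 0.8997. The change is worth making because the validity of the primary test should not depend on an unstated equal-variance assumption, and the remedy is cheap.

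**What to change.** Before database lock, choose one of two options.

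1. Keep the protocol's week-4-only crossover model as the primary analysis and use the weekly model for weeks 1–3. This needs no assumption about how spread changes over weeks.
2. Keep the merged model but let variance differ by week. For example, use `random subject` with `repeated week / subject=subject*period type=un`, name heterogeneous compound symmetry as the fallback, and specify `ddfm=kr`.

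In the weekly model under either option, add week*treatment to the MODEL statement and request the treatment difference within each week, including week 4 if that model is primary. Without this, the code does not produce the comparison that the text describes.

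Option 1 costs a sentence in SAP 11.6.1.2 and in section 12. Option 2 costs a few lines of code, 11 covariance parameters (10 unstructured plus the subject variance) against 3 now, and a stated fallback order for non-convergence. Its random subject term still imposes one between-period covariance for all week pairs. Option 2 was not simulated here; the week-4-only analysis was. That favours option 1 as the simpler choice.
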